### 5.7.3 Selection of subjects included in the analysis

As this is a single-dose treatment, we will only include dosed subjects into the analysis. In the initial analysis, all dosed subjects will be included, followed by a per-protocol analysis.

### 5.8 Randomization and blinding

# 5.8.1 Randomization list and blinding

Allocation concealment will be maintained by the lab technologist at the UHN-SHS FMT program, who will prepare the fecal filtrates for each patient but will otherwise not be involved in the conduct or analysis of the study. The allocation list will be kept in sequentially numbered envelopes with the group assignments. The group assignments will be based on a blocked randomization list (4 patients per block), created in SAS proc PLAN. The list will be created to randomize 60 patients, even though 36 are planned to be randomized. As we are including only dosed patients in the analysis, this will allow us to randomize additional patients, in case the FMT is not conducted in participants after they were randomized. The list is created by a person at the UHN, who will not be involved in conduct or analysis of the study. The technologist will have to date and sign the opened envelope.

The technologist will open the allocation on the day the patients at providing their baseline stool sample. Only if the patient is allocated to autologous FMT, a fecal filtrate from the patient's own feces is produced. On the day of the FMT, the bags with the fecal filtrate will be provided to the study team

without indication, which type of FMT is provided. Only the patient number will be on the label. Both the patient and the study team (clinical team, study coordinator, data analyst) will be blinded to group assignments.

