#### Participant withdrawal criteria:

#### All participants:

Any participant may discontinue from the study at any time:

- At the discretion of the investigator
- At the request of the participant (drop-out)

The reason for discontinuation will be clearly documented in the relevant Case Report Form (CRF).

The following will result in withdrawal of a participant from the study:

- Significant non-compliance with the protocol, based on the investigator's judgment following discussion with the study team and/or a co-investigator
- Any other situation where, in the opinion of the investigator, continued participation would NOT be in the best interest of the participant.

In the event that the participant discontinues the study due to a serious adverse event (SAE), a follow-up contact will be made. This contact will be documented in the source document.

If a participant fails to appear for a follow-up examination, up to three documented phone calls and/or registered mail will be used to locate and recall the participant, if possible.

Specific criteria for FMT recipients: Only one single dose of study product will be administered. Patients will be withdrawn from the study, if the FMT cannot be administered for any reasons. Data of these patients will not be included in the study, except for comparison with the patients who did receive the FMT. These patients will be replaced through additionally randomized patients. There will be no follow-up for patients who did not receive FMT.

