# FMT delivery

FMT by colonoscopy will be administered on one occasion using FMT derived from 150 g stool.

- Three 50 g frozen FMT, each in 30 mL conical tubes, from the same donor (i.e. a total of 150 g frozen FMT) will be thawed at 2-5°C over 24-48 hours in order to best maintain the integrity of microorganisms.
- Each thawed FMT will be diluted with sterile 0.9N NaCL to make up a total volume of 100 mL per "50g dose" and place into transport container (total volume 300 mL)
- The diluted filtrate will be transported at room temperature to the endoscopy suite in a biosafety specimen transportation bag.

- Once received by the gastroenterology team the filtrate will be administered within 9 hours throughout the colon using a colonoscope.
- Store 2 aliquots of the filtrate in 2ml vials, labelled with the same unique donor identification number, and frozen in the -80°C freezer in the event that further testing is required in the future.
- The colonoscopy procedure and post-procedure observation will otherwise follow standard medical procedures. The FMT by colonoscopy will be administered by a trained gastroenterologist.

The amount of 150 g stool suspended in 300 mL reflects the range of acceptable stool mass and volume in published literature (102). Freezing the stool up to 6 months (increasing to 12 months as soon as data from [name] lab will become available) in Normal Saline containing glycerol as a cryopreservant has been shown not to affect the efficacy against C. difficile or the viability of representative organisms (133).

Patients who are allocated to the allogenic FMT still provide a stool sample (as this is a double-blind study). The laboratory technician who is allocating the groups based on the randomization list will produce an autologous FMT only for those patients who are in this arm. The FMT products for administration will be labelled only with the study ID of the recipient, in order to keep the double-blind design. The aliquots that are kept from the lean healthy donors for future testing are labelled with the donor's study ID. Allogenic FMT will be delivered only after the corresponding donor has passed the second safety screening (same sample as the first one: stools, urine and blood).

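### Randomisation does not wait for the patient's stool to be accepted, so a shortfall that prevented dosing could exclude patients only from the autologous arm; checking stool first is a cheap, low-priority improvement

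*Combined protocol and SAP*

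**What the plan says.** **Timing of allocation.** Section 1.5 places randomisation at the point where the FMT appointment is booked and describes stool collection next. Section 5.8.1 places the opening of the envelope later: "The technologist will open the allocation on the day the patients at providing their baseline stool sample". It gives no order of steps within that day and names no acceptance check.

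**Who depends on the stool.** Section 5.8.1 states: "Only if the patient is allocated to autologous FMT, a fecal filtrate from the patient's own feces is produced". Under FMT delivery (section 1.4.2), allogenic patients also hand in stool, to protect the blind. Under stool measurements (5.6.1), 150 g is processed for FMT only in the autologous group and the donors.

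**How much stool.** Section 1.4.1 asks for a single complete stool and states no minimum weight. Section 1.5 asks for samples, in the plural, sufficient for one transplant of 150 g.

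**What happens to an undosed patient.** The withdrawal criteria in 1.3.1 say: "Patients will be withdrawn from the study, if the FMT cannot be administered for any reasons". They add: "These patients will be replaced through additionally randomized patients", and "There will be no follow-up for patients who did not receive FMT". Their data are kept for one purpose: "Data of these patients will not be included in the study, except for comparison with the patients who did receive the FMT". Section 5.7.3 sets the analysis population: "As this is a single-dose treatment, we will only include dosed subjects into the analysis". Section 5.8.1 anticipates such losses with a list of 60 slots for 36 planned patients.

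**The concern.** An analysis of dosed patients keeps the protection of randomisation if the reasons for non-dosing do not depend on the arm. One possible reason here does. A stool that is too small or stored too long matters to an autologous patient, whose dose is made from it. It does not matter to an allogenic patient, whose dose comes from a donor. If such a stool led to non-dosing, the autologous arm would be filtered on something related to the patient and the allogenic arm would not.

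Blinding the patient and the clinical team does not remove this, because the exclusion follows from which product is needed. The person who opens the envelope also prepares the filtrate, so any judgement about a doubtful stool made after opening would be made knowing the arm. Replacing the patient restores the number but not the comparability. With no follow-up of undosed patients, the effect could not be examined on outcomes afterwards.

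**Working it through.** **The plan's own figures.** Section 5.7.1 gives 18 randomised and 15 finishing per group, with 20% attrition. 18 × (1 − 0.20) = 14.4, against 15 stated. In reverse, 15/0.80 = 18.75, or 19, against 18 stated. The figures agree within rounding. (Section 1.1 says 30 randomised; 5.7.1 and 5.8.1 say 36, which is used here.) No effect size, SD or power is given, so there is no power figure to reproduce.

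**Inputs.** From the documents: 18 randomised and 15 finishing per group, two-sided 5% tests (5.7.2). Assumed, because the documents give neither:
- f, the share of the autologous arm undosed because of stool: 1, 2 or 3 of 18. The planned loss of 3 per group, for all reasons, serves only as a yardstick.
- δ, the outcome difference between undosed and dosed patients: 0.2 or 0.5 SD.

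**Formulas.** Removing a share f that differs by δ shifts the arm mean by f × δ. The standard error of the difference is √(2/15) = 0.365 SD. The type I error comes from the noncentral t distribution with 28 degrees of freedom and noncentrality f × δ / 0.365. This is a simple two-group comparison, not the planned mixed model.

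| Lost of 18 | f | Shift at δ = 0.5 | Shift / SE | Type I error, δ = 0.5 | Type I error, δ = 0.2 |
|---|---|---|---|---|---|
| 1 | 5.6% | 0.028 SD | 0.08 | 5.06% | 5.01% |
| 2 | 11.1% | 0.056 SD | 0.15 | 5.25% | 5.04% |
| 3 | 16.7% | 0.083 SD | 0.23 | 5.56% | 5.09% |

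With 3 of 18 lost, δ would have to be about 0.67 SD for the error to reach 6%.

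**Sensitivity to the selection model.** Suppose instead that the lowest share q on a latent stool-amount scale is lost, and that this scale has correlation ρ with outcome. The shift is ρ × φ(z_q)/(1 − q), where φ is the standard normal density and z_q its q quantile. For q = 5%, 10% and 20%, ρ = 0.3 gives 0.03, 0.06 and 0.11 SD, with a type I error of at most about 6% (normal approximation). The worst case tried, q = 20% with ρ = 0.5, gives 0.175 SD and 7.7%. That case implies δ = 0.175/0.20 = 0.88 SD and a loss larger than the yardstick.

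**How often it might occur.** The chance of at least one shortfall among 18 is 1 − (1 − q)^18, which is 60%, 85% and 98% at q = 5%, 10% and 20%. The expected number is 18q = 0.9, 1.8 and 3.6.

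**Cost of checking first.** To randomise 36 patients with accepted stool, 36/(1 − q) must reach the stool step: 38, 40 and 45. So about 2, 4 or 9 patients would re-collect or not be randomised.

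**The case against.** The strongest objection is that the harm needs a link that the documents do not supply. No section says that a shortfall leaves a patient undosed. Section 1.5 speaks of samples in the plural, the dose is built from three 50 g frozen units, and 1.4.4 allows filtrate to be stored for up to 3 months, so a top-up collection or a moved appointment is possible. The detailed laboratory methods and collection instructions are not in the documents. This stands: the exclusion route is possible, not established.

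A reader might infer that the envelope is opened before the stool is accepted. Section 5.8.1 fixes only the day, and randomisation in 1.5 may mean no more than assigning a sequence number. What can be said is that no acceptance step is required and that the two sections differ on when allocation occurs.

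A reader might also infer that the technologist would reject stool selectively. No section gives that person an accept-or-reject decision, and mass and storage time are objective measures.

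The mirror-image route, no released sex-matched donor dose, could exclude patients only in the allogenic arm. It depends on the donor, so if it is unrelated to the recipient's prognosis the computed shift is 0. Donor stock is not described either. A rule making randomisation wait for a donor dose is therefore not supported.

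Finally, the effect is small and every rate is assumed. Section 5.7.2 analyses change over time and allows covariates for imbalance, which the calculation ignores. The withdrawal criteria already document reasons and keep undosed patients' data, and section 6 records product use by subject. All of this supports a low priority. None of it is a reason to keep an unspecified sequence when a better one costs little.

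**Conclusion.** The concern holds as a low-priority design improvement. The plan does not make allocation conditional on an accepted stool, only the autologous arm depends on that stool, and undosed patients leave the analysis. If a shortfall led to non-dosing, the resulting exclusion would be specific to one arm.

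Under assumed losses of 1 to 3 of 18 and outcome differences of 0.2 to 0.5 SD, the type I error is about 5.0% to 5.6%. This is an illustration, not a bound: the more extreme assumptions above reach 7.7%. The documents do not support reading this as a demonstrated bias or as an invalid trial. Nor is the dosed-only analysis set itself the error; it is a deliberate choice for a single-dose treatment.

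**What to change.** 1. State in 5.8.1 that each patient's stool is checked against the protocol's own requirements, whatever the arm, before the envelope is opened. Reconcile 1.5 with 5.8.1 on when allocation occurs.
2. Reconcile 1.4.1 (a single complete stool) with 1.5 (150 g), so that the check has one criterion for amount.
3. Tabulate patients randomised but not dosed by arm and reason, with processing failures listed separately and with baseline HOMA-IR and BMI. The withdrawal criteria already keep these data; only the by-arm table is new.

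**Cost.** A sentence in 5.8.1, aligned wording in 1.4.1 and 1.5, and one table. Every patient already brings stool, but the check is not free: patients who would have been allogenic, and could now be dosed whatever their stool, would also have to pass it. At assumed shortfalls of 5%, 10% or 20%, 38, 40 or 45 patients would have to reach the stool step to randomise 36.

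**What remains.** Autologous filtrate is made only after the envelope is opened, so processing failures stay specific to that arm. The change reduces arm-dependent exclusion but does not remove it.

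Separately, 1.4.3 starts the diet adjustment 5 to 7 days before colonoscopy, while 1.4.4 requires stool before that adjustment yet accepts it up to 3 to 4 days before the procedure. Those passages should be reconciled, as a point of their own.

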### 5.8.2 Unblinding

The code for a patient will be broken, if a serious adverse event occurs that is likely due to the study product, e.g. a new infection of a recipient with a communicable disease, and where the further examination of the incident cannot be delayed until the end of the study based on clinical judgement. The breaking of the code for one patient will not affect the blinding of the other patients during the study. However, it may compromise the blinding during data analysis. In order to maintain the highest blinding level possible, only the study physician with the respective expertise (e.g. [name] and [name] for infections) will be unblinded if required for treatment of the patient. The rest of the study team will not be informed.

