### **1.7 Statistical Considerations**

### 5.7.1 Sample size and power calculations

Our sample size is determined based on current literature, feasibility and the experience of team members, due to the pilot nature of the proposed study. Following common practice for this kind of studies (e.g. (179, 180)), we plan to recruit until we have randomized 36 eligible patients (18 per FMT

group). With a 20% attrition rate we assume that 15 patients per group will finish the intervention. This represents a greater sample size than the only previous FMT study on metabolic syndrome (26). We are confident that this sample size will allow us to investigate the stated aims.

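### Section 5.8.2 says one code break leaves every other patient's blinding unaffected; with the printed fixed block of 4 it can shift the odds for up to three of them

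*Combined protocol and SAP*

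**What the plan says.** Section 5.8.2 allows a patient's code to be broken for a serious adverse event that is likely due to the product and cannot wait until the study ends. It then states: "The breaking of the code for one patient will not affect the blinding of the other patients during the study". The one risk it concedes is to blinding at the data analysis stage. It limits who is told: "only the study physician with the respective expertise" is unblinded, and "The rest of the study team will not be informed".

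Section 5.8.1 describes the list: "The group assignments will be based on a blocked randomization list (4 patients per block), created in SAS proc PLAN". It adds: "The allocation list will be kept in sequentially numbered envelopes with the group assignments". On length it says: "The list will be created to randomize 60 patients, even though 36 are planned to be randomized". Varying block sizes are not mentioned. The same section counts the clinical team among those who are to stay blinded.

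Section 5.7.1 plans 36 randomized patients, 18 in each group.

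**The concern.** In a balanced block of known, constant size, allocations depend on one another. Anyone who knows the block size and one allocation knows something about the rest of that block. The block size is printed in the protocol, and the person told the code is a study physician. The sentence in 5.8.2 allows for none of this, since the limitation it concedes concerns data analysis only.

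What could be at stake is judgement about other patients, not the laboratory measurements. Section 7.2.2 asks for adverse events to be classed as related or not related, and the withdrawal criteria in section 1.3.1 rest on investigator opinion. If the unblinded physician contributed to such decisions for a block-mate, a better-than-chance guess at the arm could colour them.

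**Working it through.** **Inputs**
- Block size 4, constant: section 5.8.1.
- 36 patients, 18 per group: section 5.7.1; 5.8.1 also gives 36. Section 1.1 gives 30, but the within-block figures do not depend on the total.
- List length 60: section 5.8.1.
- Two patients per arm in each block: inferred from 18 per group, not stated.
- Physician can place patients in envelope order: assumption. The documents do not say that the patient number follows the envelope number.

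**The plan's own figure.** 36 / 4 = 9 full blocks, and 9 × 2 = 18 per group, as stated. The full list has 60 / 4 = 15 blocks. The plan gives no number for the blinding sentence; read literally, it implies that every other patient stays at 1/2.

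**One code broken, block membership known.** A 2:2 block has 6 possible orderings. Fix one patient in arm A. Of the three others, one is in A and two are in B, and each is equally likely to be the one in A. So for each block-mate

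P(opposite arm) = 2/3 = 66.7%, against 50% before.

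This holds whichever position was revealed. Expected correct guesses among the three rise from 3 × 1/2 = 1.5 to 3 × 2/3 = 2.0. None of the three becomes certain. Patients in the other 8 of 9 blocks are unaffected.

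**One code broken, envelope order known but block boundaries not.** The revealed patient is last in the block with probability 1/4, and the next patient then starts a new block:

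P(next patient in opposite arm) = 3/4 × 2/3 + 1/4 × 1/2 = 5/8 = 62.5%.

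**Two codes broken.** Within one block, two patients share an arm with probability 1/3, and the other two allocations then follow with certainty. The base rate is low:
- P(two random breaks among 36 share a block) = 3/35 = 8.6%.
- P(same block and same arm) = 3/35 × 1/3 = 1/35 = 2.9%.
- If both broken codes were allogenic, P(same block) = 1/17 = 5.9%, because each allogenic patient has one allogenic block-mate among 17 others.

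**What varying block sizes would achieve.** Use the same next-patient measure, with the sizes equally frequent and boundaries unknown. For block size b, the b − 1 positions before the last each contribute (b/2)/(b − 1), and the last contributes 1/2. The sum is (b + 1)/2, to be divided by the number of positions.
- Fixed 4: 2.5/4 = 62.5%.
- Mix of 4 and 6: (2.5 + 3.5)/10 = 60.0%.
- Mix of 4, 6 and 8: (2.5 + 3.5 + 4.5)/18 = 58.3%.

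**The case against.** The strongest reply is that 5.8.2 is about containment, and on that it is sound. Allocations sit in separate envelopes, so opening one opens no other. One physician is told, and the rest of the team is not. After a single break nobody knows another patient's arm. All of this stands and limits the size of the point.

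It is also fair that the 2/3 needs knowledge the documents do not clearly give the physician. Product labels carry only the patient number, and its relation to the envelope number is not described.

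A reader might infer that the unblinded physician is the one who judges relatedness or withdrawal for other patients. The documents do not show this. Section 5.8.2 speaks of a physician with expertise suited to the event. Section 7.1 gives safety monitoring to the coordinator and the sponsor-investigator, and section 7.2.2 names no assessor of relatedness.

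Nor is there a shown route to the main outcome. HOMA-IR is calculated from laboratory glucose and insulin (section 1.6.3). The depression and anxiety scales are administered by the coordinator (section 1.6.5), who is not told of the break.

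Finally, varying block sizes reduce the next-patient figure by only a few points. That is correct, and it is why the wording has to change as well.

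None of this makes the sentence in 5.8.2 true as written. It is unqualified, and the risk it concedes is a different one.

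**Conclusion.** The sentence in 5.8.2 is untrue as an absolute, and the defect is minor. One break moves up to three patients from 50% to 66.7% for the opposite arm, or the next consecutive patient to 62.5% if boundaries are unknown. If 5.8.2 is followed, this information reaches one physician only. Certainty about others needs at least two breaks in one block, both in the same arm, or three breaks in one block. For two random breaks among 36 the chance is 1/35. The figures rest on 2:2 blocks and on the physician knowing envelope order, neither of which is stated.

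A reader might go further and conclude that the double blind fails once a code is broken, or that the stated protection does not exist. The documents do not support that: the restriction on who is told is real, and a single break discloses no other allocation.

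**What to change.** 1. For envelopes not yet opened, generate the list with randomly varying block sizes known only to the person who creates it.
2. Move the block size out of the protocol that the clinical team reads and into a restricted randomization document.
3. Reword 5.8.2 to say that a code break reveals no other patient's allocation directly but can carry some information about neighbouring ones. Add that relatedness of other patients' adverse events is recorded by an investigator who is still blinded, where one is available.

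The cost is one new list, replacement of unopened envelopes and a short text change. The leak is reduced, not removed: 62.5% falls to 60.0% with a 4/6 mix, so item 3 is needed even if items 1 and 2 are adopted. Balance may also suffer slightly. 36 is a whole number of blocks of 4, whereas an incomplete last block can leave the arms differing by up to half the largest block size (2 for blocks of 4, 3 for blocks of 6).

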# 6 PRODUCT ACCOUNTABILITY

The laboratory technician at Mount Sinai Hospital is responsible for study product accountability, as long as the study is blinded. The technician will maintain current, complete, and accurate records accounting for all study product produced, use of study product by each subject, and product disposition. Records of product dispensed to each subject should include the product lot or batch number, subject number, subject initials, amount dispensed, and date. Records of product disposition should include records of destruction [rendering product unusable by destroying primary packaging (i.e. packaging in direct contact with product)] or return of expired or excess study product. As soon as the study is unblinded, the investigator or designee will take over the responsibility for the product accountability.

